Sample size. Our sample size is calculated based on estimated differences of intervention effects between two arms on the primary outcome: CAPS total score at 4 months, or treatment end. The CAPS total score is a continuous measure (0-136) and reflects a combined score reflecting symptom frequency and symptom severity. A recently published yoga pilot study for patients with PTSD⁹ found a pre-treatment CAPS score of 77.33 (standard deviation = 28.6). Post-treatment scores were reduced by 34% (CAPS = 51.1, SD = 27.6, effect size = 0.9) from the yoga intervention. We powered on a medium effect size of 0.55 which requires a larger sample size than 0.9. We recognize the correlation of outcomes from subjects within the same yoga class may reduce the effective sample size compared to the same sample with independent observations. This possible “clustering effect” has implications for power. Randomization will occur at the individual not cluster or clinic level. Also, we expect that the intra-cluster correlation (ICC) will be near zero because groups will have a mixture of participants from the various recruitment sites: therefore, there is no reason to believe that participants within groups would be more correlated on the outcomes than participants from different groups. We have no preliminary data to estimate the intra-cluster correlation (ICC) for participants within the same group. However, based on similarly designed published studies, we expect the ICC to be relatively small and balanced across the two treatment arms since the cluster sizes will be similar. We will assume an ICC of 0.05 for both groups. We will also assume a 20% difference between treatment groups. The absolute score difference at 4 months is estimated to be approximately 15.4 points (61.6, 80% of 77). Assuming a common standard deviation of 28 and using a two-sample t-test, we will need 60 evaluable subjects in each arm to detect such a difference (Cohen’s $d = 0.55$) with >85% power and 5% Type I error rate. With approximately 8 subjects per treatment group/class session or cluster, the design effect is $1 + (8-1) \times 0.05 = 1.35$. Therefore, we will inflate our sample size by 35% to accommodate the potential clustering effects. We then need 81 evaluable subjects in each arm. With an assumed 30% attrition, we will then need $(81 \times 2) / 0.70 = 232$ subjects (116 in each arm).

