Data analysis: Baseline characteristics of the RELIEVE sample. To evaluate representativeness, we will compare enrollees and those who decline enrollment on baseline characteristics (socio-demographic variables, psychiatric comorbidity, and current and prior PTSD treatments). Any differences will be considered when interpreting results of subsequent analyses. We will also examine differences in baseline characteristics between patients who remain in the study and those who dropout. The linear mixed modeling approach (see next section) will ensure that all available data are used for subjects who have missing data. The models will also incorporate dropout status to adjust for follow-up missing data pattern. All participants will have baseline data. The possible missing data patterns will be (1) missing 4 month, not 7 month, (2) missing 7 month, not 4 month, (3) missing both 4 and 7 months, and (4) complete data.

Main analysis of the primary outcome. Our main analysis will use the ANCOVA (analysis of covariance) approach to linear mixed modeling of repeated measures in which the baseline measure of the relevant outcome scores (i.e., CAPS or PCL) is adjusted as a covariate in the model.⁸⁵ The model for CAPS will be adjusted for baseline CAPS score. The model for PCL, a continuous measure with a possible range of 17-85, will be adjusted for baseline PCL score. The CAPS and PCL are measured at every time point (baseline, 8 weeks, 4 months, 7 months) except the CAPS is not administered at 6 weeks in order to reduce participant burden, since the CAPS and PCL are highly correlated. We plan an intent-to-treat analysis with the primary endpoint at 4 months and evaluation of “early” response at 8 weeks and “sustained” response at 7 months (3 months post-intervention). The models will simultaneously incorporate three post-baseline measures (8 weeks ([PCL only], 4 months, and 7 months) of the relevant response variable. The main predictors will be group (treatment arm), time (categorical with indicator variables to avoid restrictive assumption of linearity over time), and their interaction. A random intercept will be used to adjust for the potential clustering effect for patients in

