Analysis of secondary outcomes. Since RELIEVE is not specifically powered for secondary outcomes, these results should be interpreted cautiously unless they are highly significant ($p < .001$). PTSD-specific symptoms (anger, sleep) and PTSD-related symptoms/outcomes (well-being/QOL, depression, anxiety, pain) will be analyzed using the linear mixed modeling approach described above for the primary outcome. The secondary outcomes will be PTSD-specific symptoms including: anger (STAXI score), sleep (MOS score) and PTSD-related symptoms/outcomes: depression (BDI score), anxiety (STAI score), well-being/QOL (SF-12), and pain (BPI). Since there will be a number of secondary outcomes, we will adjust for multiple-comparisons by using the false discovery rate (FDR)⁸⁶ method to control the overall false positive rate at 0.05. Exploratory analyses of potential mediators/moderators: interoceptive awareness and self-regulation. Moderation effects will be assessed by testing two-way interactions between intervention group membership and demographic and baseline scales including treatment credibility, interoceptive awareness, self-regulation and type of trauma (combat vs non-combat related), mTBI. Mediation effects will be analyzed using the MPLUS structural equation modeling (SEM) software to test the direct, indirect, and total effects of paths in a multilevel SEM model that includes potential mediators measured at various study points (see table of measures) including client satisfaction, interoceptive awareness and self-regulation. Adherence to the interventions and home practice will also be assessed for its dose-response effects on the primary and secondary outcomes.

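### Dropout status is to enter the outcome models in an unstated form, and no stated sensitivity analysis departs from missing at random

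*Combined protocol and SAP*

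**What the plan says.** All of this is in section 8.0, Statistical Considerations, unless noted.

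- **Baseline characteristics paragraph.** The mixed model will use all available data. Then: "The models will also incorporate dropout status to adjust for follow-up missing data pattern". Four patterns follow, defined by the 4- and 7-month visits only; the third is "3) missing both 4 and 7 months". The plan does not say whether the term is a covariate, an interaction with arm and visit, or part of a separate analysis.
- **Main analysis.** "We plan an intent-to-treat analysis with the primary endpoint at 4 months". "The main predictors will be group (treatment arm), time" and their interaction. The baseline score is a covariate, class and subject have random intercepts, and other outcome-related covariates are allowed.
- **Secondary outcomes.** These "will be analyzed using the linear mixed modeling approach described above for the primary outcome".
- **Missing data.** A logistic model will relate missingness to arm and demographics. The mixed model is said to be unbiased under MAR when the missingness mechanism is ignored, and open to bias under MNAR. The sensitivity analysis compares 100 imputed data sets with the same modelling without imputation. No imputation model is given.
- **Visit schedule (section 5.0 table).** PCL is taken at baseline, 8 weeks, 4 months and 7 months. CAPS is taken at screening, 4 months and 7 months. The main-analysis text labels the skipped CAPS visit as 6 weeks, but the table and the model description show that it is the 8-week visit. The reason given for skipping it is participant burden, "since the CAPS and PCL are highly correlated".
- **Sample size.** "We then need 81 evaluable subjects in each arm"; "With an assumed 30% attrition", the total is 232.

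**The concern.** There are two linked gaps.

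First, dropout is a post-randomisation variable. If treatment changes symptoms and symptoms drive dropout, conditioning on dropout removes part of the treatment effect from the arm contrast. The plan's own statement about MAR means that the term is not needed for validity. Nor can it help patients absent at both CAPS follow-ups: with baseline as a covariate and no 8-week CAPS, they contribute no outcome row to the CAPS model.

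Second, the plan raises MNAR and then answers with a comparison that, as stated, includes no departure from MAR. Standard imputation and the mixed model both rest on MAR, so agreement between them would not show how far the 4-month conclusion depends on it. With 30% loss budgeted and participants who cannot be blinded, that question will be asked.

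**Working it through.** **Reproducing the plan's figure.** Difference 15.4, SD 28, two-sided 5%, 85% power: 60 per arm by the normal approximation. 60 × 1.35 = 81. (81 × 2)/0.70 = 231.4, rounded up to 232. The sample size is not in dispute.

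**Effect of a dropout covariate (simulation).**

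- From the plan: effect 15.4, SD 28, 30% lost by 4 months (81 evaluable of 116), design effect 1.35.
- Assumed: baseline correlation 0.5; between-visit correlation 0.7; a further 5-10% of those remaining lost by 7 months; the 30% early loss depends on baseline CAPS (log-odds 0.5 per SD).
- Model: random-intercept ANCOVA on 4- and 7-month CAPS, maximum likelihood, 400,000 per arm, class intercept omitted.

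Estimated 4-month effect when late loss depends on the observed 4-month CAPS:

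| Late loss | Log-odds per SD | Without term | With term | Shift |
|---|---|---|---|---|
| 5% | 1.0 | 15.46 | 14.98 | 0.5 |
| 5% | 1.7 | 15.41 | 14.34 | 1.1 |
| 10% | 1.0 | 15.39 | 14.53 | 0.9 |
| 10% | 1.7 | 15.41 | 13.61 | 1.8 |

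At log-odds 0.5 per SD the shift is about 0.1 points (5% late loss) to 0.3 (10%). If late loss depends on the score relative to its arm mean, both models return about 15.4.

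**Power.** SE = 28 × √(1 − r²) × √(2 × 1.35/81), and power = Φ(effect/SE − 1.96). The worst case (10%, 1.7) was re-simulated at each baseline correlation r:

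| r | SE | Power without term (15.4) | Worst-case effect | Worst-case power |
|---|---|---|---|---|
| 0.3 | 4.88 | 88.5% | 13.2-13.3 | 77-78% |
| 0.5 | 4.43 | 93.6% | 13.6 | 87% |
| 0.7 | 3.65 | 98.8% | 14.1 | 97% |

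**MNAR tipping point.** If the 30% missing yoga values are worse than MAR implies by δ, the difference becomes observed − 0.30 × δ. With the SE held fixed, significance is lost at δ = (observed − 1.96 × SE)/0.30.

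- r = 0.5, observed 15.4: (15.4 − 8.68)/0.30 = 22.4 points; 22.4/28 = 0.80 SD.
- r = 0.5, observed 12: (12 − 8.68)/0.30 = 11.1 points, 0.40 SD.
- r = 0.7, observed 15.4: 27.5 points, 0.98 SD. r = 0.3: 19.5 points, 0.70 SD.
- No baseline adjustment (SE 5.11): 17.9 points for 15.4 and 6.6 for 12.

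The planned comparison of imputed with unimputed results would reveal none of these values.

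**The case against.** The strongest reply is that the four patterns are themselves the intended departure from MAR, a pattern-mixture analysis left under-specified. That may be so. But no pattern-by-arm terms, averaging over patterns or identifying assumption is stated. Two of the four patterns have no 4-month CAPS, and one has no post-baseline CAPS at all, so its effect cannot be estimated without an assumption that the plan does not make.

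Other points on this side stand in part:

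- A reader might infer that the plan contradicts itself because the list of main predictors has no dropout term. The documents do not support that: the same list leaves out the baseline score and random intercepts, which are in the model. What is supported is that the form is unspecified.
- If the imputation used 8-week PCL, it would rest on a weaker MAR assumption than the CAPS-only model and could be informative. Imputation can also be run under MNAR. Neither is stated, and adding PCL alone would still assume MAR.
- The logistic model of missingness and the completer-dropout comparison are useful diagnostics. They cannot test dependence on unobserved outcomes.
- PCL and the secondary outcomes have 8-week data, so the argument about patients without any post-baseline value applies to CAPS only. No shift was calculated for the other outcomes.
- The size of the shift depends on the scenario. Log-odds of 1.0-1.7 per SD are odds ratios of about 2.7-5.5, which is strong dependence.

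**Conclusion.** The point holds and should be fixed before results are seen. The plan commits its models to a post-randomisation term of unstated form, and no stated analysis departs from MAR although MNAR bias is named.

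In the scenarios examined, a literal covariate moves the 4-month CAPS contrast by 0 to 1.8 points out of 15.4 at a baseline correlation of 0.5, always towards no difference. Whether power stays above the planned 85% depends on the baseline correlation, which the plan does not give: in the worst scenario it does at 0.5 and 0.7 and does not at 0.3. The late-loss rates, correlations and dropout mechanisms are assumptions.

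Two stronger readings are not supported. A reader might infer that the term invalidates the primary analysis or favours yoga; its form is not stated, and the calculated shifts are modest and conservative. A reader might also infer that the planned result would be fragile under MNAR. At the planned effect it takes a shift of about 0.8 SD in the missing yoga values to lose significance (baseline correlation 0.5), so that effect is fairly robust. An observed 12 points, with a tipping shift of about 0.4 SD, is less so. The defect is that the plan includes nothing that would show which case applies.

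**What to change.** 1. Take dropout status out of the primary CAPS and PCL models and out of the secondary-outcome models that reuse them. Use the four patterns descriptively, or in a sensitivity analysis with a stated identifying assumption and the arm contrast averaged over patterns. Collapse sparse patterns: at 5-10% late loss, the group seen at 4 but not 7 months would hold about 81 × 0.05 = 4 to 81 × 0.10 = 8 patients per arm.
2. Keep the 100 imputations, state that they assume MAR, and give the model: run by arm, with baseline CAPS, 8-week PCL, 4- and 7-month CAPS and PCL, the stratification factors (gender, veteran status), and class or a method that respects class clustering.
3. Pre-specify one MNAR sensitivity analysis of 4-month CAPS. Either use delta adjustment with a tipping point, or impute missing yoga values from the control-arm model. Set delta in SD units, because the sample-size paragraph uses a 0-136 scale while section 5.0 describes a DSM-5 CAPS. To cover the planned effect, the range should pass about 0.8 SD at a baseline correlation of 0.5 and about 1.0 SD at 0.7.

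The cost is SAP wording and a little more analysis work, with no new data and N = 232 unchanged. The delta steps must be fixed in advance, and a fragile result may be shown to be fragile.

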Following informed consent and once a participant has been screened and meets inclusion criteria a baseline assessment will be performed. Participants will then be randomly assigned to either the holistic yoga program (HYP) or the wellness lifestyle program (WLP). The randomization process will be directed by [name]. (statistician) using a program within the REDCap database. Randomization will be stratified by gender (men vs. women) and veteran/non-veteran status. Within strata, randomization with block sizes of 4 will be executed to ensure balance. Once an eligible participant has signed informed consent, been screened, and has completed the baseline measures the project coordinator will obtain the randomization from the REDCap database. The participant identifier and date are recorded. To ensure allocation concealment, only the project coordinator, [name] and [name] will have access to the randomization function within REDCap (and will not conduct outcome assessments). The research assistant who will conduct outcome assessments will be blinded to group assignment. No one will be allowed access to randomization assignment until all baseline measures have been completed.

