8.0 Statistical Considerations

RELIEVE will involve a 2-arm, parallel group, RCT. Since participants cannot be blinded to treatment assignment, observed outcomes (if positive) could be affected by expectation bias. To account for this potential bias, we will assess treatment expectations at baseline and account for them in our analyses. We will

randomize at the patient level rather than the provider level for two reasons (1) randomization at patient level saves sample size; and (2) patients from the same provider in the two arms will be adjusted for “provider effect.” Contamination will also be low because there is relatively minimal involvement required of VA providers in RELIEVE. In addition, randomization will be stratified by veteran and non-veteran status and gender (4 strata) to avoid potential imbalance of these factors between the two arms. [name], PhD (statistician) will create a randomization scheme in REDCap for each of the four strata to randomize patients in blocks of 4 assignments within each of 4 stratum.

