a specific yoga group. And a subject-specific random intercept (nested within the group effect) will accommodate the correlation among repeated measurements from the same patient. Aim 1 will involve testing intervention effects by using the appropriate contrast from the model to test the difference in CAPS score and PCL score between the two treatment arms at 8 weeks (early response), 4 months (the primary end point which occurs immediately post intervention), and 7 months (sustained effect of intervention). Descriptive statistics including adjusted means, SD, and effect sizes (differences between two arms on adjusted means divided by pooled SD) will be reported for outcomes at each time point. Variables that are either known, or shown with our data, to be significantly correlated to the outcomes, will be considered as covariates, irrespective of their degree of baseline imbalance between randomized groups (e.g., combat vs. con-combat PTSD, baseline credibility score, and mTBI).

Secondary analysis of primary outcome. For the CAPS and PCL total scores, we will also report a clinically relevant descriptive statistic in which we define the patients with more than 30% reduction from baseline as “responders.” We will then compare the probability of responders between treatment arms using a generalized linear mixed model with a logit link. The responding status of each patient at 8 weeks (for PCL only), 4 months and 7 months will be used as the outcome variables. Main predictors are group (treatment arm), time (8 weeks for PCL only, 4 months and 7 months) and their interaction. A significant coefficient of group indicates a significant odds ratio of being a responder between the two arms.

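### The primary mixed model commits to neither randomisation stratification factor and leaves its other covariates partly open: name the strata and close the list, keeping baseline expectation

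*Combined protocol and SAP*

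**What the plan says.** Section 4.0 (Enrollment/Randomization): "Randomization will be stratified by gender (men vs. women) and veteran/non-veteran status", in blocks of 4 within strata. Section 8.0 repeats this: "randomization will be stratified by veteran and non-veteran status and gender (4 strata) to avoid potential imbalance of these factors".

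The main analysis of the primary outcome in Section 8.0 is a repeated-measures linear mixed model adjusted for the baseline score of the outcome being analysed. Its named terms are: "The main predictors will be group (treatment arm), time (categorical with indicator variables to avoid restrictive assumption of linearity over time), and their interaction". It adds a random intercept for class and one for subject. The paragraph on baseline characteristics adds dropout status. The secondary outcomes follow the same route: they "will be analyzed using the linear mixed modeling approach described above for the primary outcome".

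On other covariates, the same section says: "Variables that are either known, or shown with our data, to be significantly correlated to the outcomes, will be considered as covariates", and this is to be done "irrespective of their degree of baseline imbalance between randomized groups (e.g., combat vs. con-combat PTSD, baseline credibility score, and mTBI". The opening of Section 8.0 is firmer about one of these examples: "we will assess treatment expectations at baseline and account for them in our analyses". It also speaks of adjusting for a provider effect, which does not reappear in the model description. Neither gender nor veteran status is named as a model term anywhere.

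**The concern.** An analysis normally reflects the factors by which patients were randomised. Stratification removes between-arm variation due to those factors. A model that leaves them out still counts that variation in its standard error, so the standard error is too large and some precision bought by the design is lost.

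Here the strata are neither in nor out. An analyst could admit them as known correlates, or could note that the clause only undertakes to consider such variables and that its three examples include neither factor. Two analysts could follow the text and report different primary models.

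The same applies to the other covariates. Variables found in the trial's own data to be correlated with outcome cannot be identified until outcomes exist, and the text does not say whether that is done before or after the arm comparison is seen. Baseline expectation is promised in one paragraph and is only an example in another.

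**Working it through.** **1. The plan's own figure.** Inputs from Section 8.0, Sample size: difference 15.4, SD 28, 5% Type I error (taken as two-sided), power above 85%. n per arm = 2 × 28² × (1.960 + 1.036)² / 15.4² = 59.4, rounded up to 60. Power at 60 per arm is 85.4% by the normal approximation and 84.8% by the exact t. Design effect 1 + 7 × 0.05 = 1.35; 60 × 1.35 = 81; 162 / 0.70 = 231.4, rounded up to 232. The stated N reproduces, and it assumes no covariate adjustment.

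**2. Cost of leaving out the strata.** Work in SD units with d = 0.55, 81 evaluable per arm, classes of 8 and ICC 0.05. The variance splits into 0.95 (individual) and 0.05 (class). A class of 8 contributes 8 × 0.05 = 0.40 to the per-patient variance of an arm mean, and 0.95 + 0.40 = 1.35 is the plan's design effect. Let B be the share of individual-level variance explained by the baseline score and R the further share explained by the strata. Neither is in the documents; both are assumed.

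- Variance the model reports without strata: V_omit = 0.95(1 − B) + 0.40
- True variance when strata are balanced, also the reported variance when they are included: V_incl = 0.95(1 − B − R) + 0.40
- Type I error, omitted = 2[1 − Φ(1.96 √(V_omit / V_incl))]
- Power, included = Φ(0.55 / √(2V_incl/81) − 1.96)
- Power, omitted = Φ((0.55 − 1.96 √(2V_omit/81)) / √(2V_incl/81))

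Example, B = 0 and R = 5%: V_omit = 1.35 and V_incl = 0.95 × 0.95 + 0.40 = 1.3025. The effective critical value is 1.96 × √(1.35/1.3025) = 1.995, so Type I error is 4.60%. The standard errors are 0.1793 and 0.1826. Power is Φ(0.55/0.1793 − 1.96) = 86.6% with strata and Φ((0.55 − 1.96 × 0.1826)/0.1793) = 85.8% without.

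| B | R | Type I, omitted | Power included | Power omitted | Loss (points) |
|---|---|---|---|---|---|
| 0 | 1% | 4.92% | 85.61% | 85.46% | 0.2 |
| 0 | 5% | 4.60% | 86.58% | 85.80% | 0.8 |
| 0 | 10% | 4.21% | 87.79% | 86.25% | 1.5 |
| 25% | 1% | 4.90% | 91.51% | 91.38% | 0.1 |
| 25% | 5% | 4.52% | 92.39% | 91.75% | 0.6 |
| 25% | 10% | 4.04% | 93.45% | 92.23% | 1.2 |

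Random 30% attrition lets some imbalance back in. Simulating blocks of 4 in four strata at N = 232 returned 32% to 33% of the unstratified imbalance. Replacing R by about 0.7R in the true variance moves Type I error to 4.94%, 4.72% and 4.44% for B = 0 and changes the power loss by at most 0.3 points. If R is instead taken as a share of the whole variance at an effective 60 per arm, R = 10% gives Type I error 3.9% and power 86.6% against 88.8%. The direction and order of size are the same.

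**3. The covariate clause.** Simulation under the null with 40,000 trials per setting, N = 162, independent observations, baseline score explaining 25% of variance, and three independent candidate covariates (the number of the plan's examples). Each candidate correlates 0, 0.15 or 0.25 with outcome (assumed). Monte Carlo standard error is about 0.11 to 0.15 points.

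| How covariates are chosen | 0 | 0.15 | 0.25 |
|---|---|---|---|
| Fixed rule: p < 0.05 for pooled correlation with outcome | 5.1% | 4.9% | 5.1% |
| Better result of with or without the selected covariates | 5.2% | 6.0% | 7.5% |
| Best of all 8 subsets | 6.1% | 7.6% | 10.4% |

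A separate simulation (120 patients, 6,000 runs, three candidates each explaining 3% or 8% of variance) gave 4.8% to 5.2% for the fixed rule and 7.9% to 10.3% for free choice of subset.

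**The case against.** The strongest reply is that little is at stake. Permuted blocks already protect balance on the strata, the model already adjusts for baseline score, and the loss from omitting the strata is small under every assumption tried. That stands: a reader might infer that omission biases the result or inflates false positives, but the error runs the conservative way.

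A reader might also infer that there is no rule for choosing covariates. That is not so. The plan gives a prognostic criterion, significant correlation with outcome, and disregards baseline imbalance between arms, which is right. Part of the clause, on variables already known to matter, can be settled before any data exist.

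The most tempting reading is that the clause inflates Type I error to 6% to 10%. Those figures need someone to pick the model with the arm effect in view. No part of the plan proposes that, and the rule applied mechanically to pooled data is nominal. They are limits for a practice the text fails to exclude, not a forecast.

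What remains is narrower. The strata are uncommitted. The timing, threshold, candidate list and binding force of the clause are unstated. The two statements on expectation differ in strength.

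**Conclusion.** The point holds as a gap in pre-specification with a small, inexpensive gain in precision, not as a validity failure. Neither stratification factor is a committed term in the primary or secondary linear mixed models. Leaving them out gives Type I error of about 4.0% to 4.9% and costs about 0.1 to 1.5 points of power. This rests on an assumed 1% to 10% of individual-level variance explained by the strata, ICC 0.05, classes of 8 and strata that stay balanced; attrition adds at most 0.3 points to the loss. The sample size of 232 is unaffected.

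The covariate clause is sound in principle and nominal if applied as a fixed, arm-blind rule. It needs closing because the text does not say that it will be applied that way.

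**What to change.** **Main change.** In Section 8.0, include gender and veteran status as fixed effects in the linear mixed models for CAPS, PCL and the secondary outcomes, either as two main effects or as the four-level stratum. If they are also added to the logit model for responders, say so and note that the conditional odds ratio then changes meaning, not only precision.

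**Supporting change.** Replace the part of the clause that admits variables found in the trial data with a closed list of baseline covariates, fixed before any outcome is seen by arm. Make the baseline expectation/credibility score a fixed term, as the opening of Section 8.0 promises. It is scheduled at baseline in the Section 5.0 measures table, and Section 4.0 says "No one will be allowed access to randomization assignment until all baseline measures have been completed", so it is a legitimate pre-randomisation covariate. State whether combat status, mTBI and the provider effect are in or out.

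**To settle separately.** Dropout status arises after randomisation. Decide whether it belongs in the primary model or in a sensitivity analysis.

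**Editorial only.** The random class intercept is described for a yoga group. Since the sample-size paragraph assumes the same ICC in both arms, this is most likely shorthand; it could read as a class in either arm.

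**Cost.** Wording only, since the strata are already held for randomisation. The model spends two degrees of freedom on main effects, or three on the four-level stratum, plus those for listed covariates. A covariate listed without sight of outcomes may prove uninformative.

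### The main model's class effect is worded for yoga groups only, although the sample size assumes clustering in both arms; the stratification factors are also not named in that model.

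*Combined protocol and SAP*

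**What the plan says.** In Section 8.0, Main analysis of the primary outcome, the class term is given in a sentence that runs over a page break. It begins "A random intercept will be used to adjust for the potential clustering effect for patients in" and continues "a specific yoga group. And a subject-specific random intercept (nested within the group effect"). The other model terms are the baseline score, arm, time and the arm-by-time interaction.

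The Sample size paragraph of the same section treats clustering as a feature of both arms. It opens with "We recognize the correlation of outcomes from subjects within the same yoga class" but goes on: "we expect the ICC to be relatively small and balanced across the two treatment arms since the cluster sizes will be similar". It then states "We will assume an ICC of 0.05 for both groups" and inflates each arm by 1.35.

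Section 5.0 describes weekly in-person group classes in both programs. Both run continuously so that participants can start without waiting for a cohort. That section mentions assignment to a class, but not which participants form one cluster.

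Sections 4.0 and 8.0 both say that randomisation is stratified by gender and veteran status. Neither factor is listed in the main model. A general clause says that variables correlated with outcome will be considered as covariates; its examples are trauma type, credibility score and mTBI.

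**The concern.** The design pays for clustering in both arms, but the primary model as worded corrects for it in one. A class effect in only one arm is a recognised model, used when only one arm is delivered in groups, so an analyst could code the sentence as it stands. Any correlation among participants in the same WLP class would then be treated as independent variation. The standard error of the arm difference would be too small and the false-positive rate of the primary test above its nominal level. The secondary outcomes use the same modelling approach and would inherit the problem.

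The strata work in the opposite direction. When randomisation is balanced on a factor that predicts outcome and the model omits it, the standard error tends to be slightly too large. That costs precision; it does not threaten validity.

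**Working it through.** **Inputs, all from Section 8.0, Sample size:** difference 15.4 CAPS points; SD 28; "power and 5% Type I error rate", with power above 85%; ICC 0.05; "With approximately 8 subjects per treatment group/class session or cluster"; "With an assumed 30% attrition". Sidedness is not stated; two-sided is assumed because it reproduces the plan's figure.

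**The plan's own figure.** n per arm = 2(1.96 + 1.036)² × 28² / 15.4² = 59.4, so 60. Design effect D = 1 + (8 − 1) × 0.05 = 1.35. 60 × 1.35 = 81. 162 / 0.70 = 231.4, so 232. The plan's sample size reproduces.

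**Effect of a yoga-only class term, z approximation at one time point.** With n evaluable per arm and clustering in both arms, the true variance of the difference is proportional to 2D/n. A yoga-only class term assumes (D + 1)/n. The ratio of true to assumed SE is r = √[2D/(D + 1)]. The SE is too small by 1 − 1/r, and the Type I error is 2[1 − Φ(1.96/r)].

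The plan does not say whether 8 per class counts enrolled or evaluable participants. Both cases are shown: 8, and 8 × 0.70 = 5.6. ICC 0.05 is the plan's value; 0.01 and 0.10 are assumptions.

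| ICC | Evaluable per class | D | r | SE too small by | Type I error |
|---|---|---|---|---|---|
| 0.05 | 8 | 1.35 | 1.072 | 6.7% | 6.7% |
| 0.05 | 5.6 | 1.23 | 1.050 | 4.8% | 6.2% |
| 0.01 | 8 | 1.07 | 1.017 | 1.6% | 5.4% |
| 0.01 | 5.6 | 1.046 | 1.011 | 1.1% | 5.3% |
| 0.10 | 8 | 1.70 | 1.122 | 10.9% | 8.1% |
| 0.10 | 5.6 | 1.46 | 1.089 | 8.2% | 7.2% |

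**Simulation with estimated variance components.** REML, 4-month outcome only, 81 per arm, fixed class membership, ICC 0.05, 20,000 trials per setting (Monte Carlo SE 0.1-0.2 points). Type I error:

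| Classes per arm | Reference | Yoga-only term | Both-arms term |
|---|---|---|---|
| 10 | z | 7.1% | 5.8% |
| 10 | t, 18 df | 5.5% | 4.4% |
| 15 | z | 6.5% | 5.4% |
| 15 | t, 28 df | 5.3% | 4.4% |

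With t, the yoga-only model gives 3.6% (18 df) and 4.2% (28 df) at an assumed ICC of 0.01, and 7.4% and 6.8% at an assumed ICC of 0.10.

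**Power with the class term in both arms.** At 81 evaluable per arm, ICC 0.05 and 8 per class, SE = 28 × √(2.70/81) = 5.11 and 15.4/5.11 = 3.01. Power is Φ(3.01 − 1.96) = 85.4%, which is the plan's own level. With small-sample degrees of freedom, ten classes of 8 per arm (18 df) give about 81%. With 5.6 evaluable per class there are 81/5.6, or about 14-15, classes per arm; the SE is 4.88 and power is about 86%.

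**Strata.** The documents do not say how much outcome variance gender and veteran status explain. If they explained 2% to 10% of residual variance (assumed), the Type I error without them would be 2[1 − Φ(1.96/√(1 − R²))], or 4.8% to 3.9%.

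**The case against.** The strongest reply is that this is a drafting slip which the plan itself resolves. The Sample size paragraph also speaks of a yoga class and then applies the ICC to both arms. The main model nests every subject intercept within the group effect, which fits all patients only if every patient has a class. That reading is the likelier one. It does not remove the point, because the plan also uses the word group for treatment arm, and no sentence states a class effect for WLP.

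The second reply is that the size depends on a z reference that the plan never specifies. That stands in part. Even the both-arms model runs at 5.8% under z with ten classes, so the wording itself adds about 7.1 − 5.8 = 1.3 points. With t, the literal reading stays at 5.3-5.5%. The plan also says that it expects the ICC to be near zero, where the effect disappears.

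The third reply is that the covariate clause could admit gender and veteran status, since its examples are not exhaustive. It could, but it does not commit to them.

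A reader might go further and infer that rolling entry leaves so few classes per arm that class cannot be separated from arm. The documents do not support that. Section 5.0 names several possible venues, allows additional sessions and refers to assignment to a class. The number of classes is simply not given.

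**Conclusion.** The point holds as a wording defect in the primary model that should be fixed. Only the literal reading does harm, and the harm is modest. At the plan's ICC of 0.05, the SE is about 5-7% too small and the Type I error about 6.2-6.7% by the z approximation. In simulation with ten classes per arm it is 7.1% under z and 5.5% with small-sample t, against 5.8% and 4.4% for the both-arms model. These figures are for one time point with fixed classes; they are not a fit of the full baseline-adjusted repeated-measures model.

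Omitting the strata is conservative and loses precision of a size the documents do not give.

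Two stronger readings should be resisted. One is that the sample size is wrong: it is not, since the 1.35 inflation already covers both arms. The other is that the sponsor chose to ignore WLP clustering, or that the primary test is invalid: the plan's statements about ICC in both arms point the other way.

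**What to change.** 1. In the class-effect sentence of Section 8.0, replace the reference to a yoga group with a specific HYP or WLP class.
2. Include gender and veteran status as fixed effects in the main models.
3. As a supporting clarification, state how rolling entrants are grouped into classes for the random intercept.

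The first two are SAP wording only; the third also needs class assignment to be recorded, if it is not already. N stays at 232. Intervals will be slightly wider than under the literal yoga-only model, and power at 81 evaluable per arm stays at 85.4% (normal approximation, ICC 0.05, 8 per class).

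Small-sample degrees of freedom are optional and involve a trade-off. If the sponsor adopts them, the plan should state the resulting power beside its target of more than 85%: about 81% with ten classes of 8 per arm, or about 86% with 5.6 evaluable in each of about 14-15 classes per arm.
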